## 6. Analysis Populations and Subgroups

### 6.1 Analysis Populations

#### Total Set (TOT)

The Total Set consists of all patients who provided informed consent or assent as documented by a date of informed consent or date of assent on the 'Informed Consent' Electronic Case Report form (eCRF) page.

#### Screening Failures

Screening Failures are defined as patients who provided informed consent or assent but did not receive any Study Treatment during this OLE-IEDAT study (no "Date performed" on the "EDS-EP Infusion" eCRF page at any visit). Any data collected for Screening Failures are listed.

#### Safety Analysis Set (SAF)

The Safety Analysis Set consists of all patients who provided informed consent or assent and who received any dose of study medication during this OLE-IEDAT study (i.e., "Date performed" given on the "EDS-EP Infusion" eCRF page at any visit). The Safety Analysis Set is used for all safety analyses.

#### Full Analysis Set (FAS)

The Full Analysis set comprises *all patients who enter study IEDAT-03, have a baseline efficacy assessment in study IEDAT-03, and who received at least one dose of study medication and had at least one post-baseline efficacy assessment of the ICARS in this extension study.*

### 6.2 Treatment Misallocation

Not applicable for this single arm study.

### 6.3 Subgroup Definitions

Patients are grouped by their treatment group in the ATTeST study: EDS-EP Low Dose, EDS-EP High Dose, Non-switch Placebo, Visit 9 Low Dose, Visit 9 High Dose, Visit 12 EDS-EP Low Dose, and Visit 12 High Dose. All outputs contain columns to display these groups.

The following endpoints are also summarised by subgroups for Age (<10; ≥10 years) and Region (India; Europe, Australia, and Tunisia; United States):

- ICARS
- mICARS
- RmICARS
- CGI-C
- CGI-S
- EQ-5D-5L

Patients with a treatment gap of greater than 76 days between the ATTeST study and the OLE-IEDAT study are presented as a separate subgroup for outputs as outlined in Section 10.

## 7. Definition of Time Points and Analysis Variables

### 7.1 Definition of Time Points

The monthly infusions should be performed every 21-28 days. A window of + 10 days will be permitted on each of the scheduled monthly visits. Therefore, no EDS-EP infusion should be performed less than 21 days or more than 38 days after the previous infusion. The window between an infusion and the subsequent one should be kept as regular as possible throughout the study, avoiding fluctuations in administration windows. The date of an infusion is not bound to the date of the initial treatment but to the date of the previous IMP administration. Infusions should not be skipped; therefore, if necessary, the infusion schedule can be modified to conform to the above guidelines.

All patients who discontinue will be required to return for a Safety Follow-up Visit approximately 60 days ( $\pm$  7 days) after their last infusion.

Data collected outside of the per-protocol windows are included in the analyses based on the nominal visit label in the CRF.

'Table 2: Study Visits' shows how the Visits are labelled in all TLF outputs.

**Table 2: Study Visits**

| Scheduled Visit        | Scheduled Visit Label | Scheduled Study Day         | Visit Window                   |
|------------------------|-----------------------|-----------------------------|--------------------------------|
| Visit 0                | Screening             | -30 - -1                    | Study day $\leq$ -1            |
| Visit 1                | Baseline              | 0                           | Study day = 0                  |
| Visit 2                | Month 1               | 28                          | Study day in [21 – 38]         |
| Visit 3                | Month 2               | 56                          | Visit 2 + [21 – 38] days       |
| Visit 4                | Month 3               | 84                          | Visit 3 + [21 – 38] days       |
| ...                    | ...                   | ...                         | ...                            |
| Visit x                | Month x-1             | 28(x-1)                     | Visit x-1 + [21 – 38] days     |
| Safety follow-up visit | Safety FU             | 60 days after last infusion | Last Infusion + [53 - 67] days |

The visit schedule of the first 12 months is repeated for subsequent visits.

Unscheduled Visits are labelled as "Unscheduled Visit y" with y in (1, 2, 3,). Data from unscheduled visits are presented in listings.

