#### 13.2 Vital Signs

Vital signs assessments will be performed as specified on the Schedule of Visits and Assessments and will include body weight, temperature (oral or tympanic, according to the specific medical practice of the Center), pulse, systolic and diastolic blood pressure, and respiratory rate. Height will be measured by a stadiometer in triplicate at each required visit, and used along with body weight (also measured in triplicate at each required visit) to calculate Body Mass Index (BMI). Pulse and blood pressure will be measured after the patient has been in the supine position for at least 5 minutes.

If a change of *clinical relevance* from pre-dose to post-dose is observed, the vital signs assessment should be repeated as often as needed, at the discretion of the Investigator. Guidelines for clinically notable vital signs values are provided in [Appendix 4](#). Findings should be documented on the Vital Signs section of the Case Report Form.

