### 13.5 Special Laboratory Evaluations

Measurement of selected “special” laboratory parameters has been included in the study to evaluate potential effects of dexamethasone (EDS-EP) treatment (for details on aseptic procedure for blood withdrawal and on blood diversion see “Study Procedures on Sterility Testing for Study IEDAT-03-2018 (OLE-IEDAT)”; [Appendix 9](#)). The following special laboratory parameters will be assessed in the study:

- Blood glycosylated hemoglobin (HbA1c, %), CD4+ lymphocytes and C-reactive protein (CRP)– to be performed at Months 6 and 12.
- Screening for adrenal insufficiency will be performed in all patients, regardless of weight, via early morning (before 8:00 AM) plasma cortisol testing at the following times: (1) when patients are symptomatic, and (2) when patients are at most risk for adrenal insufficiency and adrenal crisis, such as following discontinuation or interruptions of dexamethasone dosing (i.e., loading failures and following discontinuation of the study drug). If the 8:00 AM cortisol level is below 3-5 µg/dL (depending on assay) regardless of symptoms, or the patient exhibits signs or symptoms of adrenal insufficiency ([Appendix 12](#)) and has a cortisol <10 µg/dL, the patient will receive a high dose ACTH stimulation test, regardless of weight, within 24 hours. If the ACTH stimulation test is normal, the patient can continue dosing with EDS-EP, after the effects of the ACTH have dissipated (e.g., 30 days after ACTH administered). If the patient fails the ACTH stimulation test they will be discontinued from the study and referred to a pediatric endocrinologist, with a recommendation to prescribe stress dose steroids.

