### Number of infusions received

Number of infusions received is derived as the total number of infusions completed, as determined by response to “Was EDS-EP infusion completed”, during the OLE-IEDAT study. This count includes unscheduled visits.

In addition, as the number of infusions during the ATTeST study varies with the original treatment arm, and the timing of the switch from placebo to active, the total number of infusions from the ATTeST baseline is also calculated.

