#### **Adverse Events During COVID-19 treatment interruptions**

For patients with treatment interruptions that result in gaps in dosing of greater than 60 days, adverse events are only considered treatment emergent if they occur within 60 days following the last dose. Adverse events that occurred greater than 60 days following the last dose will not be considered treatment emergent. For this population of patients whose long treatment interruption was due to COVID-19, three types of summarizations will be prepared:

- On dose (treatment emergent) adverse events
- Off dose (not treatment emergent) adverse events. Off dose events are those that occur during a period >60 days following a dose and prior to the immediately following dose.
- Restart (TEAE after restart of treatment) adverse events. Restart events are those that occur on/after the first dose after an off-dose period and prior to the start of any following off dose period.

Times to be considered as treatment interruptions due to Covid-19 are provided by EryDel in form of an excel spreadsheet.

|   |         |  |
|---|---------|--|
| CD+4 Lymphocyte count   | x10E9/L | Month 6 and Month 12   |
| Early morning Plasma Cortisol testing for Adrenal Insufficiency | µg/dL   | As needed: when patients are symptomatic, and when patients are at most risk for adrenal insufficiency and adrenal crisis, such as following discontinuation or interruptions of dexamethasone dosing |
| High dose ACTH stimulation test                                 | µg/dL   | As needed: In the event that patients show signs or symptoms of adrenal insufficiency during the study  |

All laboratory assessments are performed at local laboratories. Quantitative laboratory results are converted to their respective Reporting units for use in summary tables. Assessment of results as being within the normal range are made by the local laboratory. *Any laboratory abnormalities meeting the definition of an adverse event should be recorded on the Adverse Events CRF.*

Clinically notable values of standard laboratory are derived based on SI units as outline in Appendix 13.1.

If repeat tests are performed at any visit the result documented under the nominal visit label is used in all summaries and analyses for that Visit.

Baseline is as described in Section 7.1.

The change from baseline is calculated for quantitative laboratory tests at each scheduled post-baseline visit as:

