## Vital Signs

*Vital signs assessments are performed pre- and post-infusion at all visits with additional triplicate pre- and post-infusion assessments every 6 months as specified on the Schedule of Visits. Vital Sign assessments include body weight, temperature (oral or tympanic, according to the specific medical practice of the Center), pulse, systolic and diastolic blood pressure, and respiratory rate. Height will be measured by a stadiometer in triplicate at each required visit and used along with body weight (also measured in triplicate at each required visit) to calculate Body Mass Index (BMI). Pulse and blood pressure will be measured after the patient has been in the supine position for at least 5 minutes. All results are recorded on the ‘Vital Signs Pre-Infusion’ or ‘Vital Signs Post Infusion’ eCRF pages.*

The baseline value is as described in Section 7.1. The arithmetic mean of all triplicate values is calculated for use in summary tables. Results are converted for summary tables as follows:

- Temperature: Results measured in Fahrenheit converted to Celsius as
  - $\text{Temperature (}^\circ\text{C)} = (\text{Temperature (}^\circ\text{F)} - 32) * 5/9$
- Weight: Results measured in pounds converted to kilograms as
  - $\text{Weight (kg)} = \text{Weight (lb)} / 2.205$
- Height: Results measured in inches converted to centimetre as
  - $\text{Height (cm)} = \text{Height (in)} * 2.54$

The change from baseline is calculated for vital signs with a continuous response at each scheduled post-baseline visit:

- $\text{Change from baseline} = \text{Scheduled Visit result (measured or derived)} - \text{Baseline value.}$

At each scheduled post-baseline visit each vital sign with a continuous response is derived as having a clinically notable change using the rules in Table 5.

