### 10.7.2 Clinical Laboratory Evaluation

Separate listings for hematology, chemistry, urinalysis, hemolysis panel and the special laboratory parameters present the raw values, normal ranges, investigators interpretation (for special laboratory parameters only) and, for all quantitative tests, the results converted to SI units for the SAF. Special laboratory data for adrenal insufficiency screening, early morning plasma cortisol and ACTH stimulation test are listed separately for the SAF.

Data for each parameter of a continuous nature are summarized, separately for hematology, chemistry and the special laboratory parameters, for the SAF. The change from baseline to each visit is calculated and summarized. Data for each parameter of a categorical nature is summarized descriptively using absolute counts (n) and percentages (%).

Clinically notable changes in laboratory values are summarized separately for hematology, chemistry and urinalysis using absolute counts (n) and percentages (%).

Results of the investigators interpretation of special laboratory parameters are presented as a shift table comparing each visit to Baseline for the SAF.

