### 10.7.6 Vital Signs

All Vital Sign data are included in a listing for the SAF.

Vital Sign results and change from baseline are summarized by summary statistics on scheduled visits for the SAF. The absolute counts (n) and percentages (%) of patients with clinically notable findings are included in a separate summary for the SAF. The absolute counts (n) and percentages (%) of patients with at least one clinically notable change from baseline and summary statistics of the most extreme clinically notable increase and decrease from baseline are presented in separate summaries for the SAF.

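### Vital signs from visits labelled unscheduled stay out of the SAP's 'at least one' and 'most extreme' notable-change tables; the laboratory notable-value tables appear to be affected in the same way

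*SAP*

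**What the plan says.** **Unscheduled visits.** SAP 7.1 labels these visits separately and, under Table 2, says: "Data from unscheduled visits are presented in listings". Data collected outside a visit window keep their nominal label and stay in the analyses.

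**Vital signs.** SAP 7.4.8 says: "At each scheduled post-baseline visit each vital sign with a continuous response is derived as having a clinically notable change", using the limits in SAP Table 5. SAP 10.7.6 summarises results and changes on scheduled visits. It then asks for patients with "at least one clinically notable change from baseline and summary statistics of the most extreme clinically notable increase and decrease from baseline". The output is Table 14.3.3-2.2.

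**Laboratory.** The laboratory text in SAP 7.4.8 computes change from baseline at each scheduled post-baseline visit and adds: "If repeat tests are performed at any visit the result documented under the nominal visit label is used in all summaries". Notable values follow SAP Appendix 13.1 and are counted in Tables 14.3.2-2.1 to 2.3 (SAP 10.7.2).

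**Protocol.** Section 13.2 provides that, after a clinically relevant change from pre-dose to post-dose, "the vital signs assessment should be repeated as often as needed, at the discretion of the Investigator". Section 13.4 has clinically significant abnormal laboratory tests repeated where needed.

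**The concern.** The primary endpoint is safety, and SAP 3.4 names changes in vital signs and laboratory parameters as part of it. A reader of a table headed by 'at least one' or 'most extreme' will assume that it covers everything recorded after baseline. If it covers scheduled visits alone, it omits measurements that may have been taken because something was wrong. Nothing in the planned table tells the reader so. The counts would then be too low, and the reported extremes could be milder than values that sit in the listings of the same report.

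**Working it through.** The plan states no figure for this point, so the check is mainly a comparison of rules.

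**1. Vital signs.**
- Input to the table: a notable change, which SAP 7.4.8 derives at scheduled post-baseline visits.
- Values from visits labelled unscheduled: sent to listings by SAP 7.1.
- Output: patients with one or more derived notable changes, and the most extreme of them (SAP 10.7.6).

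No step brings an unscheduled value into the derivation, so it does not reach Table 14.3.3-2.2.

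**2. Is there an exception?** There is one, for exposure. On the number of infusions, SAP 7.4.6 says: "This count includes unscheduled visits". So the SAP says when it wants unscheduled visits counted, and no vital-sign or laboratory text contains a similar sentence. An infusion given at an unscheduled visit adds to exposure, while the vital signs taken around it go to a listing.

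**3. Laboratory.** The listing rule in SAP 7.1 has no laboratory exception, and a repeat test yields to the value under the nominal label. No rule readmits the worst post-baseline value. This points the same way as step 1. However, neither the sentence on notable laboratory values nor the text for their tables contains a scheduled-visit limit. Appendix 13.1 and the start of the laboratory section are also absent from the available text. The laboratory part is therefore likely but not proven.

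**4. Vital-sign repeats within one scheduled visit.** SAP 7.1 covers assessments repeated because the EDS process was repeated, and the rule in SAP 7.4.8 covers laboratory tests. Neither says which value is used when vital signs are repeated under Protocol 13.2. The SAP is silent here.

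**5. Direction.** Adding values to a patient's record can leave an 'at least one' flag unchanged or switch it on, but never off. The patient's own extreme can stay or move outward. So the restricted count is at or below the full count. The mean of the extremes across patients could move either way, because newly counted patients may bring milder values.

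**6. Size.** Let k be the number of patients whose only notable value lies at an unscheduled visit or in an unused repeat. The percentage changes by 100 × k / N. Protocol 16.2.1 gives a maximum N of 150. The documents do not give k, so 1 to 10 is an assumed range.

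| k | 100 × k / 150 |
|---|---|
| 1 | 0.67 points |
| 5 | 3.33 points |
| 10 | 6.67 points |

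Since 150 is the maximum, 0.67 points is the smallest effect one patient can have. It is larger in each of the seven ATTeST treatment-group columns, whose sizes the documents do not give.

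**The case against.** **Repeats usually follow an abnormality already seen.** If the value that prompted the repeat is notable and stays under the nominal label, the patient is already counted. Omitting the repeat loses a patient only if the first value missed the limit and the repeat met it, or if the site recorded a milder repeat as nominal. This stands. It limits the effect of repeats on the count, but not the effect on the most extreme value, nor the effect of unscheduled visits.

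**There is another route into the tables.** Laboratory abnormalities that qualify as adverse events are recorded as such and enter the adverse event tables whatever the visit label. That is true, but it depends on the investigator's judgement, and SAP 3.4 makes vital-sign and laboratory changes a separate part of the endpoint.

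**The study is descriptive, and Protocol 16.2.5 commits to identifying and listing notable values.** This also stands. The point is a gap in the SAP's summaries and not a breach of the protocol.

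**Discretionary testing differs between investigators.** Counts that use every value may be harder to compare across groups. This is a real cost of the fix and needs a footnote.

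A reader might also infer four stronger things that the documents do not support:
- *Every unscheduled record is left out.* The infusion count includes unscheduled visits, and out-of-window data keep their nominal label.
- *Triggered tests have no way into a summary.* The scheduled-visit restriction is explicit for vital signs only, and the treatment of same-visit vital-sign repeats is left open.
- *Adrenal risk has no summary result.* SAP 10.7.2 says: "Special laboratory data for adrenal insufficiency screening, early morning plasma cortisol and ACTH stimulation test are listed separately for the SAF". But SAP 7.4.8 names cortisol suppression and events indicative of adrenal insufficiency as events of special interest, and these are tabulated (Table 14.3.1-1.4).
- *The share lost follows from abnormality duration divided by visit spacing.* That ratio describes what monthly sampling would miss, not what the unscheduled records would add.

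**Conclusion.** The point holds for vital signs. As written, the SAP keeps values from visits labelled unscheduled out of Table 14.3.3-2.2, so that table can understate notable changes and need not show the most extreme recorded value. For the laboratory notable-value tables the same effect is probable, subject to Appendix 13.1. The direction for patient counts is certain (equal or too low). The size is unknown: at least 0.67 percentage points per affected patient, with the number of such patients not given. The conclusion assumes that sites use the unscheduled label for extra contacts and that the programmers follow the text literally. This is an inexpensive improvement to a primary safety summary, not a flaw that undermines the trial.

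**What to change.** Keep all by-visit tables on nominal visits. Amend SAP 7.1, 7.4.8, 10.7.2 and 10.7.6 to state that the patient-level 'at least one', any-time and 'most extreme' notable-value summaries for vital signs and laboratory tests (Tables 14.3.3-2.2 and 14.3.2-2.1 to 2.3) use all post-baseline values, including unscheduled and repeat ones. State also how vital signs repeated within one scheduled visit are handled. Add a footnote that the summaries include measurements made at the investigator's discretion, whose frequency may differ between investigators and groups.

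The cost is SAP wording and modest programming on data already collected. Counts will rise somewhat, and comparison across groups becomes less clean.

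As a separate and optional addition, one patient-level table could count patients tested for early-morning cortisol, patients below the limits in Protocol 13.5, patients given an ACTH test and patients with an abnormal response. The existing eCRF pages hold these data.

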### Date of First OLE-IEDAT Infusion

The Date of First OLE-IEDAT Infusion is defined as the earliest value of the "Date performed" recorded on the 'EDS-EP Infusion' eCRF page, provided "Was EDS-EP infusion started within 30 min of completion of the EDS Process?" is answered with "Yes".

### Date of Last Infusion

The Date of Last Infusion is defined as the latest value of the "Date performed" recorded on 'EDS-EP Infusion' eCRF page, provided "Was EDS-EP infusion started within 30 min of completion of the EDS Process?" is answered with "Yes".

### Date of First Infusion of Active Treatment

The Date of First Infusion of Active Treatment is defined as the earliest infusion of active study drug, including infusions from the ATTeST study. For patients in the Non-Switch Placebo group

this will equal the date of first OLE-IEDAT Infusion. For all other patients this date will be received by CROMSOURCE in ADaM datasets from ATTeST.

### Intervals from First Infusion of Active Treatment

Efficacy analysis outlined in Section 7.4.7 is displayed in 6-month intervals from first dose of active study drug, using data from the ATTeST Study.

These are derived by calculating day since First Infusion of Active Treatment:

$$\text{Day since First Infusion of Active Treatment} = (\text{Date of visit} - \text{Date of First Infusion of Active Treatment})$$

This is then mapped to 6 months intervals as follows:

| Interval  | Window            |
|-----------|-------------------|
| 6 months  | Day in [91, 273]  |
| 12 months | Day in [274, 456] |
| 18 months | Day in [457, 638] |
| 24 months | Day in [639, 821] |
| ...       | ...               |

Any day since First Infusion of Active Treatment < 91 will not be mapped to a 6-month interval.

